Heated hand: The heated hand vein technique is used to obtain blood samples that are “arterialized”, meaning they are more like arterial blood than venous blood. Using the heated hand vein technique is standard procedure used during stable isotope tracer infusion studies to ensure proper assessment of substrate kinetics. The heated hand vein technique avoids the use of more invasive procedures such as an arterial line.

Blood sampling: Procedure is necessary to assess the concentrations of labeled and unlabeled fatty acids in order to calculate hepatic synthesis-secretion rates for omega-3 DHA. Previous work in this area has been performed successfully in rodents, but has not been translated to humans in a clinical trial.

Storage of Patient Samples: The storage of clinical samples is necessary for collaboration and assurance of similar analysis conditions across all of the study samples.

Qualifications of Investigators – Infusion Substudy

Introduction

Enrollment in the Infusion Substudy will require a new informed consent, obtained via a face-to-face meeting with [name] and/or [name], CRNP, MS.

The Brain Physiology and Metabolism Section (BPMS) of the National Institute on Aging (NIA), of which [name] is Chief, is collaborating on the d5-LNA Infusion Amendment. The BPMS conducts basic and clinical research related to factors that regulate brain function and structure in health and disease. One focus is to identify the influence of dietary composition and liver metabolism of polyunsaturated fatty acids (PUFAs). Methods are developed to image regional brain metabolism of omega-6 AA and omega-3 DHA in unanesthetized animals and in humans (with positron emission tomography), and to quantify the ability of the liver to synthesize these PUFAs from their precursors LA and LNA, respectively, *in vivo*. The BPMS has developed the infusion methodology and analysis in rodents, which is a basis of this clinical amendment.

D5-LNA Infusion Amendment Collaborators

[name]., is Chief of the BPMS NIA, who has published extensively in the areas of lipid metabolism and brain function in health and disease. He received his MD degree from Harvard Medical School, and is clinically credentialed at the NIH Clinical Center. The laboratory that he directs has developed and validated the infusion method and analysis in rodents. These methods form a major basis for the Infusion Amendment employed in this human protocol. He is involved in the design of the protocol, and its conduct, and in data analysis and writing up results.

[name] will not obtain consent.

S12. Benefits

This Infusion Substudy will provide generalizable knowledge on the normal DHA synthesis-secretion rates in humans, and the impact of dietary fatty acids on hepatic synthesis-secretion of DHA. This experimental procedure has no anticipated benefits for study participants.

S13. Classification of Risk

- No direct benefit, but likely to yield generalizable scientific knowledge
- More than minimal risk
- The risks are reasonable in relation to anticipated benefits. We will obtain important insights into normal DHA synthesis-secretion rates in humans, and learn whether modifying dietary LA alters synthesis-secretion rates of DHA. Both findings could ultimately have important implications for the prevention and/or adjunctive management of conditions including addictive disorders.

S14. Consent documents and process

Who will obtain Consent

The informed consent process for the Infusion Substudy will include a face-to-face meeting with [name], [name] and/or [name], CRNP, MS.

S15. Data Safety and Monitoring & S16. Adverse Event Reporting

S15.1 Data Safety and Monitoring Board

The Infusion Substudy is two-arm study with an 8-hour intravenous infusion of a non-radioactive nutrient in a buffered solution with human albumin. Since the research procedures are to be performed in adult subjects and such procedures involve minor increase over minimal risk, the collection, monitoring and analysis of adverse events will be the responsibility of the Principal Investigator and the investigative team. No DSMB will be convened.

S15.2 Data Safety and Monitoring Plan

Elements of the Data Safety and Monitoring Plan

- (1) Monitoring mechanism:
The Principal Investigator and/or medically qualified staff will monitor the infusion protocol participant vital signs data for signs of participant distress as stated on page 44.
- (2) Frequency:
The Principal Investigator and/or medically qualified staff will be present at the beginning of the infusion and will stay on the unit for the first 2 hours of the procedure. Medically qualified staff will check the participant vital sign status at least hourly after these first 2 hours.
- (3) Stop or change rules:
Participants may choose to stop the infusion procedure at any time. Participants will be reminded to report any signs of distress or discomfort to medically qualified staff

members. Medically qualified staff will determine if any signs of participant distress are present and are severe enough to abort the infusion procedure.

(4) Advanced Plans:

As stated on page 46, this study is designed with the first primary aim as a feasibility study and the data will be reviewed after the first 4 participants.

(5) Information to be monitored for participant safety:

Participant vital signs (as stated above)

(6) Communication:

A record of participants removed from the infusion substudy will be reported to the Addictions IRB at the time of annual review. Serious adverse events will be reported according to the required NIH guidelines as stated in section S16 on the next page.

S15.3 Data Monitoring for Quality Assurance

Data monitoring for quality assurance will be the responsibility of the Principal Investigator and the investigative team.

(1) Monitoring mechanism:

The Principal Investigator and the investigative team will monitor the protocol participant free and esterified fatty acid data.

(2) Frequency:

After each infusion, the blood samples will be analyzed for deuterated fatty acid concentration and the results will be reviewed by the Principal Investigator and the investigative team.

(3) Information to be monitored:

Deuterated fatty acid concentration will be monitored for appropriateness of infusion dose, rate and sampling schedule

(4) Communication:

Infusion substudy progress will be reported to the Addictions IRB at the time of annual review in the form of a summary report. This summary report will include the numbers of recruited, and enrolled participants in this substudy. It will also include a brief data report noting any need for adjustments in the infusion procedure or sampling schedule.

S16. Adverse Event Reporting

Adverse events

In the course of a dietary study and infusion amendment, adverse events may occur. Unanticipated adverse events that occur as a direct result of research studies initiated at the NIH, but not related to the natural history of the underlying disease will be summarized at the time of the annual review.

Serious Adverse events

A serious adverse event is any adverse experience that:

1. Results in death;
2. Is life threatening;
3. Results in hospitalization or prolongs hospitalization;
4. Results in persistent or significant disability/incapacity;
5. Results in congenital anomaly/birth defect; or

6. Results in a condition, which in the judgment of the investigator represents a significant hazard.

Serious adverse events that are possibly, probably or definitely related to participation in research studies performed at the NIH Clinical Center will be reported. However, serious adverse events (other than death) that are clearly and unambiguously due to extraneous causes (accidental, environmental or coincidental events) will not be reported.

All serious adverse events will be reported using the NIH Serious Adverse Event Report Form to the NIAAA CNS IRB, and NIAAA Clinical Director as soon as possible, but no later than seven days of death or life threatening serious adverse event or within fifteen days after the occurrence of all other forms of serious adverse events.

S17. Alternatives to participation or alternative therapies

Subjects are healthy volunteers and are not recruited for the treatment of a medical condition. Participants are counseled to continue their usual medical care for the duration of the study.

S18. Confidentiality

Medical records

This information will remain confidential and protected according to NIH guidelines. Some clinically relevant research data will be stored indefinitely in the medical record and will be accessible to the patient for review by others of their choosing (doctors, insurance companies etc.) after executing a release of information.

Research Data

Data will be collected and entered on form sets labeled with a unique coded identifier that is not related to the patient's name or any other personal identifier (Soc Security number, NIH employee number, etc). Data will be kept in a locked cabinet or in secure computer files with access only for the Principal Investigator (PI) and Associate Investigators (AIs) involved with the study. When entered into the electronic databases, information will be under the CRC and NIH network regular access control. In addition, any information allowing the identification of the participants will be removed. The only possibility to reconstruct the link between database records and information will be through the unique identifier. The translation key will be stored in a locked cabinet or secure computer file with access available only to the PI and AIs named in this protocol document.

The validated psychometric instruments used in this protocol have been converted to an electronic web-based secure data entry platform) administered by the NIAAA. The security of the data management system is curated by the NIAAA IT department in agreement with NIH data security policies.

Most data generated in this study will be stored and maintained in the NIAAA clinical database which is password protected and secure.

Sample Storage

Coded blood and tissue samples without patient names or personal identifiers will be stored in secured freezers at [name] or in the NIAAA Clinical Core lab freezers in the 1-SE area of the clinical center. Samples will be processed upon completion of the study and destroyed when analysis is complete. Any additional collaborations requiring transfer of patient material will be done in a coded fashion after informing the IRB and obtaining necessary assurances from the outside institution. The protocol will be amended and IRB approval will be sought when such collaborations are established.

S19. Conflict of Interest/Technology Transfer

NIH guidelines on conflict of interest have been distributed to all investigators. There are no conflicts of interest to report. Technology transfer is not applicable to this Infusion Substudy.

S20. Compensation**Remuneration for Infusion Substudy**

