6.2 Inclusion criteria

To be eligible for this research study, participants must:

1. Be between 18 and 50 years of age.
2. Have regular menstrual cycles.
3. Be willing to use an effective method of birth control such as hormonal contraception, intrauterine device, barrier methods combined with spermicide, or surgical sterilization.
4. Have a body mass index of 25 to 35 kg/m².
5. Be otherwise healthy as determined by history, medical examination and laboratory tests.
6. Be able to come to the NIH Clinical Center every weekday for 3 months.
7. Be able to understand the consent form, and provide informed written consent.

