Diet Group	omega-6 LA*	omega-3 LNA	omega-6 AA	omega-3 EPA+DHA
A. Orange	8.00	0.40	0.045	0.045
B. Blue	1.00	0.40	0.045	0.045

Fatty acid intakes as percentages of daily food energy (en%). LA indicates linoleic acid; LNA indicates alpha-linolenic acid; AA indicates arachidonic acid; EPA indicates eicosapentaenoic acid; DHA indicates docosahexaenoic acid. *Indicates that LA will be modified as a controlled variable via isocaloric substitution for oleic acid.

Participation requires a new consent specific to the Infusion Protocol and one additional visit lasting approximately 22-hours, including:

- (1) Admission to the 5SW Metabolic Unit;
- (2) Insertion of two intravenous catheters;
- (3) Overnight fast;
- (4) 8-hour infusion of d5-LNA with serial blood sampling.
- (5) Completion of craving/hunger questionnaires.

[figure not shown]

Fig. 8. Infusion Substudy Flow Diagram: Participants in Diet Group A (8 en% as LA) and Diet group B (1 en% as LA) are invited to participate in the Infusion Substudy. Participation requires one additional 22-hour study visit after 10-12 consecutive weeks of consuming study diets. Saliva is collected for FADS genotyping in the baseline phase of the main protocol. LA indicates omega-6 linoleic acid; d5-LNA indicates deuterated omega-3 alpha-linolenic acid.

Characteristics of Stable Isotope d5-LNA Infusion

Non-radioactive stable isotope-labeled alpha-linolenic acid (17,17,18,18,18-D5, 98%) (d5-LNA) in potassium salt will be prepared by Cambridge Isotope Laboratory; the product will be tested and verified as sterile and non-pyrogenic by Cambridge before delivery to NIH. The NIH Pharmacy will then mix the d5-LNA potassium salt into sterile water and then reconstitute with 25% human albumin, and then verify the identity, purity, and dose, sterility and non-pyrogenicity of these infusion materials. These procedures are performed in order to ensure that the infusion materials meet NIH Pharmacy standards for human infusion. [name] (Chief of the Pharmaceutical Development Section) is our Clinical Center Pharmacy contact ([contact] [contact]).

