A total dosage of d5-LNA of approximately 19.2 μ mol per kg of body weight will be infused intravenously through a 0.2 micron filter at a constant rate for up to 8 hours during the feasibility stage. This initial dose estimate was calculated based on published human infusion trials (68) using deuterated palmitate and the endogenous steady state concentration of LNA in plasma (23) for an obese subject from the main protocol with body weight of 95kg. The half-life of unesterified infused fatty acids in human plasma is about 2 minutes, so that a steady state plasma concentration should be reached in about 10 minutes (5 half-lives). After the feasibility stage, we will adjust infusion rate, dose and duration.

Estimation of Plasma Volume

DEXA scans performed as part of the main protocol (11-AA-0028) will be used to estimate lean body mass for normalization of body fluid volumes as described by Boer. These estimates for plasma volume

will be used in calculating the infusion amount and rate, and in interpreting results as described in Section S.9.

Time points for Blood Collection and Fatty Acid Analysis

Timed venous blood samples will be collected from the start of d5-LNA infusion until 480 min (8 hours) to determine plasma levels of esterified and unesterified labeled fatty acids. Sampling will be at -10, -5, 0, 5, 10, 20, 40, 60, 80, 100, 120, 150, 180, 210, 240, 300, 360, 420, and 480 minutes (19 time points). A total blood volume of 80 mL will be collected. Blood samples will be used to determine the plasma concentrations over time of endogenous unesterified omega-6 and omega-3 fatty acids (nmol/ml) and d5-labeled unesterified and esterified omega-3 fatty acids (nmol/ml) and endocannabinoids with GC and GC-MS. Collected blood will be centrifuged at 2000g for 10 min, and plasma will be transferred to another tube, and kept at -80°C until assay. After lipid analysis of esterified and unesterified labeled and unlabeled fatty acids, hepatic synthesis-secretion rates will be calculated for EPA, DHA and other omega-3 fatty acids as described in Section S.9.

Genotyping

DNA is collected from sputum for analysis of FADS gene variants as part of the main protocol.

Infusion Substudy Procedure Specifics

Infusion Substudy Timeline

All study procedures are for research purposes only. The sequence of procedures is given in Table 8. All time-points are targets, and may be adjusted based on practical considerations.

Table 8: Timeline for Infusion Visit

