Participants will be withdrawn from the Infusion Substudy if they do not follow the instructions outlined in the protocol and informed consent form. Participants may also, at any time, choose to discontinue their participation from the Substudy.

S9. Outcome Measures (Infusion Substudy)

Primary Outcome Measure

Synthesis-secretion rates for omega-3 DHA with d5-LNA infusion, after 12-weeks of exposure to diets containing either 8 en% or 1 en% as omega-6 LA.

Human d5-LNA Infusion Model (adapted from [name] rodent model (64,65)).

The objective of this study is to quantify conversion rates of circulating unesterified plasma LNA into longer chain omega-3 fatty acids. It is assumed that most of this conversion will take place in the liver.

The idea is to infuse labeled d5-LNA, henceforth designated as LNA*, intravenously at a constant rate for up 8 hours, and to sample blood plasma (through a second intravenous catheter) periodically for measuring esterified and unesterified plasma concentrations of LNA* and omega-3 LCPUFAs (18:4n-3*, 20:4n-3*, 20:5n-3* (EPA), 22:6n-3* (DPA), 22:5n-3*, 24:6n-3*, and 22:6n-3* (DHA). Additionally, DEXA scan data from the primary protocol (11-AA-0028) will be used to estimate plasma volume V_{plasma} . Measurements also will be made of unesterified unlabeled LNA, DPA, EPA and DHA concentrations in plasma, to calculate actual conversion rates, as future studies may look at rates that may depend on these concentrations altered in disease or dietary states.

Initially, a constant infusion rate of approximately 2.2 umol/min will be established and infusion time will be 8 hours, for a total labeled infusion amount of 350 mg. Since the half-life of injected unesterified fatty acid is about 2 minutes in human plasma, a steady state concentration LNA* will be established within approximately 10 minutes after infusion is initiated. Duration and rate can be adjusted as necessary to properly determine the enrichment of the tracer and fatty acid kinetics.

Equations

Assuming linearity, the net rate of synthesis of a labeled omega-3 LCPUFA (e.g. DHA*) within secreted VLDLs or other lipoproteins from labeled LNA* is given as:

$$\frac{V_{plasma} dC_{DHA^*}}{dt} = \bar{k} C_{s-LNA^*}$$

The rate of disappearance of DHA* from plasma is given as:

$$\bar{k} C_{DHA^*}$$

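### The starting d5-LNA infusion is stated in two ways that differ 1.73-fold at the protocol's own 95 kg reference weight; S6 and S9 must be reconciled

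*Combined protocol and SAP*

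**What the plan says.** **Starting dose, S6 (Characteristics of Stable Isotope d5-LNA Infusion).** "A total dosage of d5-LNA of approximately 19.2" µmol per kg of body weight is to be infused at a constant rate for up to 8 hours in the feasibility stage. The estimate was worked out "for an obese subject from the main protocol with body weight of 95kg". The tracer is supplied as a salt: "d5-LNA) in potassium salt will be prepared" by the manufacturer.

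**Starting dose, S9 (Human d5-LNA Infusion Model).** The values to be used at the outset are "a constant infusion rate of approximately 2.2 umol/min will be established and infusion time will be 8 hours". The same sentence then puts the dose by mass at 350 mg. No body weight appears, and the 350 mg is not identified as salt or acid.

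**A further basis, S6 (Estimation of Plasma Volume).** Plasma volume estimates from DEXA lean mass "will be used in calculating the infusion amount and rate". No formula follows.

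**Later change, S6.** "After the feasibility stage, we will adjust infusion rate, dose and duration". S10 expects the feasibility data to come from the first four infusion participants.

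**Aim 2 quantity.** S2 and S9 name the DHA synthesis-secretion rate as the primary outcome. S6 says these rates will be calculated, by the method in S9, from labelled and unlabelled fatty acids. S9 also lets the slope of plasma volume times labelled-DHA concentration, plotted against time, approximate the coefficient. In S10, the analysis text applies the t-test to a synthesis-secretion rate from labelled-DHA data, and the sample-size text applies it to both rates and coefficients.

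**The concern.** Both dose statements describe the start of the substudy, so they should give the same infusion for the same woman. They do not, and the difference grows with body weight in a trial of overweight women. S6 has the NIH Pharmacy verify the dose of the prepared product, and the protocol offers two starting figures to verify against, plus a plasma-volume basis that is never written out.

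The analysis has a related but smaller problem. Under S9's linear model, the appearance of labelled DHA is a coefficient times the plasma level of labelled LNA. A labelled-DHA slope that is not divided by that level depends on how much tracer was given. Since the infusion is expected to change after the first few women, the test quantity should be worded so that a change of dose cannot enter the comparison of diets.

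**Working it through.** **Inputs.** S6: 19.2 µmol/kg, 95 kg, up to 8 h (480 min). S9: 2.2 µmol/min, 8 h, 350 mg. Section 6.2: "Have a body mass index of 25 to 35 kg/m"². The documents give no molar masses. I assume about 283.5 g/mol for the acid and 321.6 g/mol for the potassium salt, from the chemical formula. These affect only the mg checks.

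**1. Reproducing S9's own total.** 2.2 × 480 = 1,056 µmol.
- As potassium salt: 1,056 × 321.6 / 1,000 = 340 mg, 3% below the stated 350 mg.
- As acid: 1,056 × 283.5 / 1,000 = 299 mg, 14% below.

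S9 is therefore internally consistent, given that its rate is approximate, if the 350 mg is the weight of the salt.

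**2. S6 at its own reference weight.** 19.2 × 95 = 1,824 µmol; 1,824 / 480 = 3.80 µmol/min.

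**3. The gap at 95 kg.**

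| Reading of S9 | Total (µmol) | S6 total / S9 total |
|---|---|---|
| 2.2 µmol/min × 480 min | 1,056 | 1,824 / 1,056 = 1.73 |
| 350 mg as potassium salt | 350,000 / 321.6 = 1,088 | 1,824 / 1,088 = 1.68 |
| 350 mg as acid | 350,000 / 283.5 = 1,235 | 1,824 / 1,235 = 1.48 |

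**4. Can the wording close it?**
- Rounding: if 2.2 stands for 2.15 to 2.25, the ratio is 1.77 to 1.69.
- Duration: delivering 1,824 µmol at 2.2 µmol/min takes 1,824 / 2.2 = 829 min, or 13.8 h, beyond the 8 h limit.
- Later adjustment: S6's figure is for the feasibility stage and S9's is the initial one, so both precede any change.

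**5. Where the rates agree.** 1,056 / 19.2 = 55 kg. At BMI 25 that is a height of √(55/25) = 1.48 m; at any higher BMI the woman would be shorter still. The ratio (19.2 × weight / 1,056) is 1.27 at 70 kg, 1.45 at 80 kg and 1.64 at 90 kg. If the 350 mg governs instead, agreement is at 1,088 / 19.2 = 56.7 kg (salt) or 1,235 / 19.2 = 64.3 kg (acid).

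**6. The Aim 2 wording, side by side.**
- Pointing to a tracer-normalised rate: S6 derives the rates from labelled and unlabelled fatty acids; S9 measures unlabelled LNA so that actual conversion rates can be calculated; the last equation printed in S9 contains the labelled-LNA concentration; S9's text describes the fitted coefficient as relative to a given plasma LNA concentration.
- Pointing elsewhere, or open: S9 uses the undivided slope as an approximation to the coefficient; S10's analysis text speaks of labelled-DHA data; S10's sample-size text names two quantities for one t-test.
- Not stated: whether the first four women enter the t-test, and how they divide between diets.

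**The case against.** **On the dose.** S9's figure sits in a description of the kinetic model, while the dosing text proper is in S6, where the pharmacy verifies the dose. Both figures are approximate and both are expected to change. The substudy also describes the labelled amount as a trace. This limits what can be inferred: a reader might conclude that participants will be wrongly dosed or harmed, and the documents do not support that. It does not remove the contradiction, because the two figures are presented as starting values and step 4 shows that none of the qualifiers joins them.

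**On Aim 2.** A reader might infer that the plan tests an unnormalised labelled-DHA rate, so that changing the dose would distort the diet comparison. The documents do not support that reading. S10's sentence names the synthesis-secretion rate, S6 sends its calculation to S9, and S9 contains the ingredients for normalising. This objection largely stands; what is left is inconsistent wording. Symbols in S9's equations and the start of S10 were also damaged when the PDF was read, so no fault can be found with the units of the coefficient.

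**On power.** It is also tempting to quote a loss of power from pooling women infused at different tracer levels. That would require unnormalised rates, pooling of the first four, an assumed split by diet and an assumed size of adjustment, none of which is stated. The 1.73-fold figure is a discrepancy between two sections, not a planned change between participants, and cannot serve as that size.

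**Conclusion.** The dose contradiction holds with high confidence: 1,824 against 1,056 µmol at the protocol's own 95 kg, a ratio of 1.73, using only figures in S6 and S9. The 1.48 to 1.68 range for the mg reading rests on the assumed molar masses. The rates coincide only at 55 kg, so most plausible entrants under the BMI floor would have two different starting infusions on paper. The role of plasma volume is undefined. Nothing in the documents settles which figure was intended.

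The Aim 2 point is a secondary clarification, held with medium confidence because of the damaged symbols. The method supports a tracer-normalised rate, but S9 and S10 do not name one test quantity consistently, and the handling of the first four women is open. No claim is made that the planned test is invalid or that power is lost through pooling.

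**What to change.** 1. **Reconcile the dose in S6 and S9.** State one dosing basis and give the total in µmol, the rate in µmol/min and the amount in mg, naming salt or acid. If plasma volume enters the calculation, write the formula. Which figure is right is for the investigators to settle.
2. **Name one Aim 2 test quantity, in the same words in S9 and both parts of S10.** A form consistent with S9 is, for each woman, the labelled-DHA slope (plasma volume times rate of change of concentration), divided by her plateau unesterified plasma d5-LNA, times her unesterified unlabelled plasma LNA. Under the protocol's linearity assumption the tracer level cancels.
3. **State before the comparison whether the first four women enter the t-test.** With step 2 in place, a change of dose alone does not require excluding them. If they are excluded, restate power. The calculation behind Fig. 10 (two-sided t-test, alpha 0.05, means 14.1 and 23.547) reproduces its 0.813 at 12 per group with SD 7.762. At 10 per group, assuming two women leave each arm from the maximum of 12, it gives 0.73 at SD 7.762, 0.87 at SD 6.4684 and above 0.99 at SD 3.7647.

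The cost is wording in S6, S9 and S10. Unesterified labelled and unlabelled LNA are already to be measured, so no samples, visits or participants are added.
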